## 2.2 Secondary Objectives

The secondary objectives of the study are:

- To determine the pharmacokinetic profile of BBI608 and Cetuximab, or Panitumumab, or Capecitabine when administered in combination.
- To determine the pharmacodynamics (biomarkers) of BBI608.
- To evaluate tolerability of two dosing regimens of BBI608 by comparing administration of BBI608 at 240 mg twice daily starting dose and escalating to 480 mg twice daily after cycle 1 versus administration of BBI608 at 480 mg twice daily starting dose with dose adjustment permitted.
- To evaluate tolerability of BBI608 by comparing prophylactic administration of anti-diarrheal medication versus as needed administration of anti-diarrheal medication. The tolerability will be assessed using adverse event profile and achieved dose intensity.

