## 7.3 Treatment Compliance

A patient is considered compliant with the study protocol when study medication is administered at a compliance level of greater than 80%.

BBI608 compliance will be calculated using the following equation:

(Number of capsules actually ingested /number of capsules that should have been ingested per dose level) x 100= % compliance

Capecitabine compliance will be calculated using the following equation:

(Number of capsules actually ingested /number of capsules that should have been ingested per dose level) x 100=% compliance

Cetuximab or Panitumumab compliance will be calculated using the following equation:

(Number of treatments performed /number of treatments that should have been performed per dose level) x 100=% compliance

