### 10.8 Analysis and Sample size for sub-cohorts

Each sub-cohort will be analyzed for number of days of Grade II/III diarrhea and % treatment compliance achieved during the first two cycles. The % treatment compliance will be calculated as the number of capsules actually ingested over the number of capsules that should have been ingested per dose level multiplied by 100. The research questions addressed by sub-cohorts are hypothesis-generating and exploratory in nature. Initially 6 subjects will be assigned to each sub-cohort to assess the effect of intervention. Selected sub-cohorts will be extended to enroll up additional 20 patients. The decision of extending the enrollment will be based on clinical assessment without formal statistical testing. However, 20 patients will give 80% power to detect 20% difference in % treatment compliance between two arms and 57% power to detect the difference of 25% in the number of days of having Grade II/III diarrhea using two-sided Z test with pooled variance at type I error rate of 0.15. The control rates assumed are 70% for treatment compliance and 30% for diarrhea. The patients will be sequentially allocated to different sub-cohorts by the Sponsor to avoid section bias.

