combination arm, patients assigned to sub-cohorts IA and IB would receive napabucasin at 240 mg twice daily (480 mg total daily dose) starting on Day 1 of Cycle 1. Intra-patient dose escalation of napabucasin to 480 mg twice daily (960 mg total daily dose) was allowed for patients in these cohorts as tolerated. Patients assigned to sub-cohorts IIA and IIB would receive napabucasin at 480 mg twice daily (960 mg total daily dose) starting on Day 1 of Cycle 1. In the event of toxicity, dose adjustment of napabucasin was permitted, as recommended in dose modification guidelines. Additionally, patients assigned to sub-cohorts IA and IIA would receive prophylactic anti-diarrheal treatment starting the day prior to Day 1 of Cycle 1. Patients assigned to sub-cohorts IB and IIB would receive anti-diarrheal treatment on an as-needed basis starting with development of diarrhea (ie, any occurrence greater than the patient's baseline). For each combination regimen, patients would be sequentially assigned to each of the 4 sub-cohorts in the following order until 6 patients were accrued in each of the sub-cohorts: IA, IB, IIA, and IIB. If required, up to an additional 20 patients might be assigned to selected sub-cohorts to validate the observations in the initial 6 patients.

Sub-cohort	Napabucasin Starting Dose Level	Anti-diarrheal Administration*
IA	240 mg bid (480 total daily dose) ¹	Prophylactic
IB	240 mg bid (480 total daily dose) ¹	As needed
IIA	480 mg bid (960 total daily dose) ²	Prophylactic
IIB	480 mg bid (960 total daily dose) ²	As needed

Table 1 Tolerability Analysis of Napabucasin

¹Intra-patient dose escalation of napabucasin to 480 mg po twice daily (960 mg total daily dose) is allowed as tolerated. ²In case of toxicity, dose adjustment of napabucasin is permitted.

*See protocol amendment 2 [5] section 7.1.4 for details

A study cycle would consist of 28 days of daily administration of napabucasin in combination with cetuximab or panitumumab, or capecitabine. Cycles would continue until unacceptable toxicity, disease progression (clinical or radiological) or another discontinuation criterion is met. Pharmacokinetic (PK) assessments would be performed on the first 6 patients enrolled in each combination arm. Pharmacodynamic assessments would be performed in patients with readily accessible tumor tissue through an optional tumor biopsy. Evaluation of anti-tumor activity would be performed at 8-week intervals per RECIST 1.1 while patients remain on study.

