- Intended DI (*dose unit/time unit*) = [intended cumulative dose per cycle] / [intended number of *time units* in a cycle]
- By cycle RDI (%) = $100 \times [by cycle actual DI] / [intended DI]$
- \circ Overall RDI (%) = 100 × [overall actual DI] / [intended DI]

Note the intended dose level is fixed at the start of treatment rather than the start of a cycle

- One exception is for Cetuximab. For Cetuximab, dose level is permitted to change from 400 mg/m^2 on day 5 in cycle 1 to 250 mg/m² for each subsequent infusion. If dose level decreases for Cetuximab 4-7 days after first dose date, then updated dose level is the new intended dose level for Cetuximab.
- Second exception is for all backbone therapies. All backbone therapies incorporate BSA or weight to calculate each dose. Panitumumab incorporates weight to calculate each dose-all other therapies incorporate BSA. Therefore, the BSA to be used for calculating each dose of the backbone therapies will be using the Mosteller method (see below) based on the last available weight and height prior to each infusion. For Panitumumab, the last available weight prior to each infusion will be used for calculating each dose.
- $BSA [m^2] = ((Height [cm] \times Weight [kg])/3600) \times 0.5$
- Calculated doses will be rounded to the nearest integer
- Cumulative dose, actual dose intensity and relative dose intensity will remain missing if they cannot be derived due to missing weight, or BSA. Height from the most recent earlier visit can be used if height is missing.

The intended cumulative dose of napabucasin per cycle is calculated by (intended dose level per day) \times (intended cycle duration in days)

• Intended dose level per day for napabucasin is 500mg po BID

Dose unit of napabucasin is mg, dose unit of other combination drugs (except Panitumumab) is mg/m^2 , dose unit of Panitumumab is mg/kg.

Treatment compliance

Treatment compliance for napabucasin is defined as follows:

(Cumulative actual total dose / total planned or intended dose) $\times 100 = \%$ compliance

For any IV combination drug (Cetuximab and Panitumumab), compliance will be calculated using the following equation:

(Number of treatments administered / number of treatments that should have been administered) $\times 100 = \%$ compliance

For oral combination drug (Capecitabine), compliance will be calculated using the following equation:

(Cumulative actual total dose / total planned or intended dose) \times 100 = % compliance

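### SAP 8.2.1 replaces the protocol 10.8 sub-cohort compliance ratio with one that has no two-cycle window and an undefined denominator, and the direction of the dose-regimen comparison can depend on that denominator.

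*SAP*

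**What the plan says.** **Protocol.** Section 10.8 (repeated in the synopsis) gives each sub-cohort two measures: days of Grade II/III diarrhea, and "treatment compliance achieved during the first two cycles". Compliance is the "number of capsules actually ingested over the number of capsules that should have been ingested per dose level multiplied by 100". Section 7.3 has the same ratio for BBI608 in general. On the tolerability objectives, section 2.2 says: "The tolerability will be assessed using adverse event profile and achieved dose intensity".

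**SAP 8.2.1, treatment compliance.** For napabucasin the ratio is "Cumulative actual total dose / total planned or intended dose", times 100. No time window is attached, and the denominator is not defined there.

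**SAP 8.2.1, relative dose intensity (RDI), just above.** Two lines bear on an intended dose. One reads "Note the intended dose level is fixed at the start of treatment rather than the start of a cycle". The other sets the intended napabucasin level at 500 mg BID, with no exception for sub-cohorts.

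**SAP 8.2.1, daily treatment compliance, just below.** Four measures count days at full dose or higher, or days at any non-zero dose. Two of them use the first 56 days. The SAP does not say which measure serves protocol 10.8.

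**Regimens (protocol 2.2 and 4.1, SAP 2.1).** IA/IB start at 240 mg BID. Protocol 4.1 allows escalation to 480 mg BID as tolerated, and objective 2.2 describes it as following cycle 1. IIA/IIB start at 480 mg BID with dose adjustment permitted.

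**The concern.** The regimens being compared differ precisely in planned or permitted dose changes. A compliance ratio whose denominator follows the prescribed dose measures adherence. One whose denominator is fixed measures delivered dose. Both are legitimate, but they answer different questions, and the SAP moves from the first towards the second without saying so.

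The SAP wording also leaves several denominators open. If the planned total is a fixed daily level times actual treatment duration, the SAP ratio reduces algebraically to its own overall RDI, and no capsule ratio of the protocol 10.8 kind would be reported. At stake is the reading of one of the two measures that 10.8 assigns to the sub-cohorts.

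**Working it through.** **The plan's own figure.** The documents contain no worked compliance value. The one figure tied to this endpoint is the 80% power in protocol 10.8 for a 20-point difference with 20 patients (control 70%, two-sided alpha 0.15, pooled Z). With 20 per group and 70% v 90%, power = Φ[(0.20 − 1.44 × √(2 × 0.8 × 0.2/20)) / √((0.21 + 0.09)/20)] = 55.8%, so it does not reproduce. That is a separate matter, and nothing below depends on it.

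**Inputs.**
- Window: two cycles (protocol 10.8). SAP 2.1: "A study cycle would consist of 28 days of daily administration of napabucasin". So 2 × 28 = 56 days.
- Daily dose: 480 mg at 240 mg BID, 960 mg at 480 mg BID, 1,000 mg at 500 mg BID.
- Capsules: 80 mg after amendment 2 (SAP 2.1), so 3 or 6 per dose. With a single strength, capsule ratios and mg ratios coincide.
- Assumed: every prescribed capsule is taken.

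**Step 1. Fully adherent groups: I (IA/IB) escalated after 28 days, II (IIA/IIB) never reduced.**

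Taken by I: 28 × 480 + 28 × 960 = 40,320 mg. Taken by II: 56 × 960 = 53,760 mg.

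| Denominator | I | II | I − II |
|---|---|---|---|
| Protocol, level prescribed at the time | 40,320/40,320 = 100% | 53,760/53,760 = 100% | 0 |
| SAP, starting level | 40,320/26,880 = 150% | 53,760/53,760 = 100% | +50 |
| SAP, 500 mg BID | 40,320/56,000 = 72% | 53,760/56,000 = 96% | −24 |
| SAP, if planned means currently prescribed | 100% | 100% | 0 |

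The 500 v 480 mg mismatch alone costs a fully adherent, unreduced II patient 4 points. The change of sign comes mainly from using one common level: 480 mg BID for all would give 75% v 100% (−25), although no SAP line names that as the intended level.

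**Step 2. Not every group I patient escalates.** A never-escalated patient takes 26,880 mg: 100% against the starting level, 26,880/56,000 = 48% against 500 mg BID. If a fraction f escalates after cycle 1 and II is unreduced, the mean difference is +50f against the starting level and (48 + 24f) − 96 = 24f − 48 against 500 mg BID. For any f above 0 the signs are opposite. At f = 0.4 the differences are +20 and −38.4.

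**Step 3. Dose reductions in group II.** An adherent patient starting at 960 mg/day and halved to 480 mg/day (size and timing assumed; the protocol fixes neither):

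| Halved after | mg taken | Starting level (53,760) | 500 mg BID (56,000) | Protocol |
|---|---|---|---|---|
| Day 7 | 30,240 | 56.3% | 54.0% | 100% |
| Day 14 | 33,600 | 62.5% | 60.0% | 100% |
| Day 28 | 40,320 | 75.0% | 72.0% | 100% |

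**Step 4. Limit of the sign change.** If a fraction g of group II is halved after Day 14, the differences become 50f + 37.5g and 24f + 36g − 48. They have opposite signs only while 24f + 36g is below 48. With f = 1 that means g below 2/3. With f = g = 1 both favour group I (+87.5 and +12).

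**The case against.** **The SAP denominator may mean the dose currently prescribed.** Both intended-dose lines belong to RDI, whose purpose is to reflect reductions, and the compliance text does not import them. On that reading the two documents agree. This stands: the SAP is ambiguous, and it is not certain to give a different answer. But it leaves the denominator undefined, and the only rules a programmer would find nearby do give different answers.

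**The protocol wording is also a reading.** Neither 10.8 nor 7.3 says current level, and the sub-cohort table is headed by starting dose. If the starting level were meant, the protocol ratio would register reductions too. The prescribed-at-the-time reading is the more natural one, but it is an assumption here.

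**The SAP already has two-cycle measures.** This is right as far as it goes. A reader might infer that the SAP dropped the two-cycle window altogether. It did not: two daily measures cover the first 56 days. They count days rather than capsules, however. A full daily dose is not defined there for an escalating patient, and neither measure is tied to 10.8.

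**One patient's gap is not a group difference.** Correct. The Step 3 gaps cannot be set against the 20-point design difference in 10.8. Steps 1 and 2 are group means, but only under the stated paths.

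**The stakes are modest.** Protocol 10.8 calls the sub-cohort questions exploratory and bases extension on clinical assessment. SAP 4.1 has no hypothesis testing. The response evaluable set uses daily treatment compliance and not this ratio.

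**Conclusion.** The point holds as a mismatch of definitions with an unresolved denominator. The SAP ratio differs in wording from protocol 10.8, lacks its window, and sits beside two intended-dose rules that conflict for IA/IB if the first means the assigned starting level. The 500 mg BID line matches neither sub-cohort regimen. SAP 2.1 ties that dose to the period before amendment 2, and the sub-cohorts date from amendment 2.

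For fully adherent groups the regimen difference is 0, +50 or −24 points depending on the denominator. This assumes 56 days, escalation after cycle 1 in group I and no reductions in group II. The reversal persists with partial escalation but can disappear when many group II patients are reduced.

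Two stronger readings are tempting and are not supported:
- That the SAP inflates the escalating regimen. This follows only from the starting-level denominator; 500 mg BID deflates it.
- That a given patient scores 100% in one document and about 63% in the other. The 62.5% needs an assumed halving after Day 14 and the starting-level denominator. The range over the assumed timings is about 54-75%, and it is 100% if planned means currently prescribed.

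This should be corrected before the sub-cohort tables are interpreted. It does not affect the primary endpoint.

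**What to change.** In SAP 8.2.1:

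1. Name one compliance measure for the protocol 10.8 sub-cohort comparison and limit it to Days 1-56. Say whether the denominator runs to Day 56 or to the last dose for patients who stop early.
2. Define its denominator as the amount prescribed at each dose level, consistent with protocol 10.8.
3. Report delivered dose separately, as actual dose intensity by sub-cohort over the same window. The SAP already defines actual dose intensity, and objective 2.2 names it.
4. Reconcile the fixed-at-start line and the 500 mg BID line with each other and with the assigned sub-cohort regimens.
5. State that the daily compliance measures are supplementary, and define a full daily dose for patients whose dose changes.

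The cost is SAP wording and about one table row. The case report form is not among the documents. However, the SAP already needs actual doses for cumulative dose, and protocol 7.3 already calls for capsule counts, so new data collection should not be needed.

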## 4.6 Study Duration

Patients will receive treatment with BBI608 and Cetuximab, or Panitumumab, or Capecitabine until progression of disease, unacceptable toxicity or another of the discontinuation criteria is documented (see Section 5.6). It is expected that most patients will receive between one and four cycles of BBI608 and Cetuximab, or Panitumumab, or Capecitabine for a treatment period of 4 to 16 weeks.

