### **5.4** Tumor Evaluation Visits

Disease status and tumor response will be assessed in eight-week intervals up to one year after starting therapy (calculated from the first dose of BBI608) or as clinically indicated. Standard

imaging studies should be performed according to institutional procedures. Tumor response for solid tumors will be evaluated using the guidelines for Response Evaluation Criteria in Solid Tumors (RECIST 1.1) outlined in Section 9.

Once progression of disease during therapy is documented, patients must be taken off treatment and may receive any therapy as determined by their treating physician.

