Medical history will be coded by SOC and PT using the MedDRA version 18.0 prior to the analysis. Medical history will be summarized by SOC and PT using the number and percentage of patients

for the safety analysis set.

Duration of Overall Survival Follow-up

The duration of overall survival (OS) follow-up is defined as time from the date of first treatment to death or the last known alive visit. The median follow-up time for OS and the corresponding 95% confidence interval (using the method of Brookmeyer and Crowley, 1982 with the log-log transformation) will be summarized using the reverse Kaplan-Meier (KM) method for the safety set. The analysis involves the event and censoring rules to be switched (ie, the patients who die become 'censored', and the censored patients are treated as the 'event').

Summaries of the number and percentage of patients who have died, those still in survival followup, those lost to follow-up, and those who have withdrawn consent will be also provided.

Extent of Exposure

Exposure may be summarized as dose received (cumulative dose or actual dose intensity) or as dose received relative to the intended dose (relative dose [RD], or relative dose intensity [RDI]), or both.

The information that will be summarized depends on how the study drug is dosed (eg, infusion cyclical, oral daily, oral cyclical).

In what follows, "time unit" can be weeks or days.

Actual treatment duration = actual end of treatment date – date of first dose of study drug + 1, where

- For napabucasin and Capecitabine, the actual end of treatment date is the last dosing date
- For cyclic combination drugs in Arms A and B, actual end of treatment date = last dose of cyclic dosing + interval 1, where interval = 7 for Arm A and interval =14 for Arm B.

Cumulative dose in a cycle or overall is the sum of the actual doses received in a cycle or overall, respectively.

Actual Dose Intensity [DI]

- By cycle actual DI (*dose unit/week*) = [cumulative dose in the cycle]/ [actual cycle duration in *weeks*]
- Overall actual DI (*dose unit/week*) = [overall cumulative dose] / [actual treatment duration in *weeks*]
- Note that actual DI for cyclical dosing is calculated based on actual cycle duration in all but the last cycle where it is fixed at the intended duration.

Relative Dose Intensity (RDI): The basic intent is to evaluate dose per *time unit* factoring in dose reductions, interruptions, or delays.

Relative dose intensity (RDI) by cycle and overall

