Daily treatment compliance will be reported for each patient by dose level cohort.

- The % of days the patient received full daily dose of napabucasin or higher out of actual treatment duration in days.
- The % of days the patient received a non-zero dose of napabucasin out of actual treatment duration in days.
- The % of days the patient received full daily dose of napabucasin or higher out of the first 56 days from treatment start.
- The % of days the patient received a non-zero dose of napabucasin out of the first 56 days from treatment start.

Daily treatment compliance will be grouped according to the following categories: < 60%, $\geq 60\% - < 80\%$, $\geq 80\% - < 90\%$, $\geq 90\%$, and will be summarized for all arms.

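### No SAP measure computes the protocol's two-cycle compliance ratio for the sub-cohorts, and the two 56-day measures count days after a required stop for progression, or after death, as missed

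*SAP*

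**What the plan says.** Protocol 10.8 names two quantities for the sub-cohort analysis: days of Grade II/III diarrhea, and percentage compliance over the first two cycles. It defines compliance as the "number of capsules actually ingested over the number of capsules that should have been ingested per dose level multiplied by 100".

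SAP 8.2.1 lists four daily compliance measures for napabucasin. Two use the patient's own treatment period, for example "The % of days the patient received full daily dose of napabucasin or higher out of actual treatment duration in days". Two use a fixed window: "The % of days the patient received full daily dose of napabucasin or higher out of the first 56 days from treatment start" and "The % of days the patient received a non-zero dose of napabucasin out of the first 56 days from treatment start". Results are grouped as below 60%, 60 to below 80%, 80 to below 90%, and 90% or more. The same section defines a cumulative dose ratio and by-cycle and overall relative dose intensity (RDI).

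On stopping, Protocol 5.4 says: "Once progression of disease during therapy is documented, patients must be taken off treatment". Protocol 5.6 lists radiologic or clinical progression and death among the reasons for removal, together with unacceptable toxicity and withdrawal of consent. Protocol 4.6 adds: "It is expected that most patients will receive between one and four cycles".

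**The concern.** The sub-cohorts are there to compare the tolerability of two starting doses and two anti-diarrheal strategies (Protocol 2.2). A compliance measure used for that comparison should fall when patients cannot or will not take the drug. It should not fall because the disease progressed and the protocol ended treatment.

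The protocol's ratio has capsules due as its denominator, and it is reasonable to read this as no capsules being due once treatment must stop for progression. The 56-day measures leave those days in the denominator. With six patients per sub-cohort and sequential, non-randomized assignment, a chance imbalance in early progression or death could look like a difference in tolerability. Because the SAP does not compute the protocol's own ratio, no planned table would correct that impression.

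**Working it through.** **Inputs.** Cycle length is 28 days (SAP 2.1: "A study cycle would consist of 28 days of daily administration of napabucasin in combination with cetuximab or panitumumab, or capecitabine"), so two cycles are 2 × 28 = 56 days, which matches the SAP's window. For actual treatment duration, SAP 8.2.1 says: "For napabucasin and Capecitabine, the actual end of treatment date is the last dosing date". The documents give no numerical result for this measure that could be reproduced, and no early-stopping rate.

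**Is the denominator really fixed?** The SAP does not say expressly that 56 applies to every patient. It gives no rule that shortens it, however, and the same list contains two measures that do use the patient's own duration. The plain reading is a fixed 56.

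**Formulas**, for a patient who takes every assigned dose up to last dosing day L ≤ 56:

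- 56-day measure = 100 × L / 56
- actual-duration measure = 100 × L / L = 100%

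| Last dose (day) | 56-day measure | Actual-duration measure |
|---|---|---|
| 14 | 25.0% | 100% |
| 28 | 50.0% | 100% |
| 33 | 58.9% | 100% |
| 34 | 60.7% | 100% |
| 44 | 78.6% | 100% |
| 45 | 80.4% | 100% |
| 50 | 89.3% | 100% |
| 51 | 91.1% | 100% |
| 56 | 100.0% | 100% |

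Whatever the adherence, a last dose before Day 34 falls in the lowest category, and one before Day 45 falls below the 80% level that Protocol 7.3 uses for a compliant patient.

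**Does either type of measure separate progression from intolerance?** Take two patients who each took every dose to Day 28, one stopped for progression and one for toxicity.

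| Measure | Progression stop | Toxicity stop |
|---|---|---|
| 56-day | 28/56 = 50% | 28/56 = 50% |
| Actual duration | 28/28 = 100% | 28/28 = 100% |
| Proposed ratio (see fix) | 28/28 = 100% | 28/56 = 50% |

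Neither existing type separates them.

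**Size in a group.** If a share q of otherwise fully adherent patients stops on Day 28, the group mean is 100 − 50q. For assumed q of 10%, 20%, 30% and 40%, it is 95%, 90%, 85% and 80%.

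**Other SAP measures.** The cumulative dose ratio has no two-cycle window. The 80% rule in SAP 6.3 covers one cycle only. By-cycle RDI can be read for cycles 1 and 2, but it is a dose-intensity measure. Its intended dose is also stated as 500 mg BID, while SAP 2.1 gives sub-cohort starts of 240 or 480 mg BID. Against 1000 mg per day, a patient taking every assigned dose would read 480/1000 = 48% or 960/1000 = 96%. If the undefined full daily dose were also taken as 1000 mg, that patient would score 0% on the full-dose 56-day measure. These passages must be reconciled. The 50% in the Day 28 example holds on the non-zero-dose measure in any case, and on the full-dose measure only if full means the assigned dose.

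**The case against.** The strongest reply is that the SAP already prints the complement. For anyone who stops by Day 56, the actual-duration measure covers exactly their treatment in the first two cycles. For anyone treated longer, the 56-day measure is not distorted. Read side by side, patient by patient, the two show what happened. This is fair, and it is why the existing measures should stay. It does not close the gap: the pair gives the same two numbers for a progression stop as for a toxicity stop, and neither is the ratio in Protocol 10.8.

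A second reply concerns frequency, and it largely stands. Imaging is scheduled at eight-week intervals, with the first on-study scan before cycle 3 (Protocol 5.4 and Appendix A), so progression found on schedule appears around Day 56. A stop for progression on Day 28 needs clinical progression or unscheduled imaging.

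Third, little formal weight rests on the measure. Protocol 10.8 calls the sub-cohort questions exploratory and leaves extension to clinical judgment. SAP 4.1 plans no hypothesis test. The secondary objective names adverse events and dose intensity rather than compliance.

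A reader might go further in three ways that the documents do not support:

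- One might set the effect of one such patient on a six-patient mean, 50/6 = 8.3 points, against the 20-point difference in Protocol 10.8. That difference is sized for 20 patients, and the SAP specifies categories, not a cell mean, for this measure.
- One might spread stopping times evenly over the expected 4 to 16 weeks to estimate how many adherent patients are misclassified. The scan schedule makes that pattern unlikely before Day 56, the only period that matters.
- One might say that the protocol itself keeps days after toxicity or refusal in the denominator and drops those after progression. Protocol 10.8 does not say what is due after any kind of discontinuation.

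**Conclusion.** The gap is real but modest. SAP 8.2.1 contains no measure that returns the two-cycle ratio of Protocol 10.8. The two measures confined to that window score a fully adherent patient who stops for progression on Day 28 at 50% instead of 100%, and they score other early stops in proportion to L/56.

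This rests on three readings: that the 56-day denominator is fixed; that no capsules are due after a required stop for progression, or after death; and, for the full-dose measure only, that full daily dose means the assigned dose. The first two are reasonable inferences from the text, not express statements.

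The effect is limited to stops before Day 56, mainly clinical progression, progression on unscheduled imaging, and death. How many patients that involves cannot be derived from the documents. No primary endpoint depends on the 56-day measures. The change is worth considering because it is cheap and makes the planned sub-cohort comparison easier to interpret.

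**What to change.** Add one two-cycle measure to SAP 8.2.1 and name it as the measure for the sub-cohort comparison: napabucasin dose taken in Days 1-56 divided by dose due in Days 1-56 at the assigned dose level, times 100. End the denominator at the earliest of Day 56, documented progression or death.

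State that days after stopping for toxicity or refusal remain in the denominator, and present this as an analysis choice, not as protocol text. Define full daily dose and assigned dose level for this purpose, and reconcile the 500 mg BID intended dose with the 240 and 480 mg BID sub-cohort starts.

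Keep the four existing daily measures alongside it. If the fixed 56-day denominator is intended, say so and explain the departure from Protocol 10.8.

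The cost is SAP wording and one derived variable from dosing and disposition data. The drawback is reliance on the recorded reason for stopping in an open-label study, where clinical progression and intolerance can be hard to tell apart.
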